6.2 Discontinuation of the Site

If an investigator intends to discontinue participation in the study, the investigator must immediately inform the Sponsor.

6.3 Discontinuation of the Study

The Sponsor may terminate this study prematurely, either in its entirety or at any study site, for reasonable cause provided that written notice is submitted in advance of the intended termination. Advance notice is not required if the study is stopped due to safety concerns. If the Sponsor terminates the study for safety reasons, the Sponsor will immediately notify the investigator and subsequently provide written instructions for study termination.

7 STATISTICAL METHODOLOGY

The statistical analysis will be coordinated by the responsible Astellas Medical Affairs, Americas (MA-A) biostatistician. A Statistical Analysis Plan (SAP) will be written to provide details of the analysis, along with specifications for tables, listings and figures to be produced. The SAP will be finalized before the database soft lock at the latest. Any changes from the analyses planned in the SAP will be justified in the Clinical Study Report (CSR).

Prior to Database Lock, a Final Review of Data and TLFs Meeting will be held to allow a review of the clinical trial data and to verify the data that will be used for analysis set classification. If required, consequences for the statistical analysis will be discussed and documented. A meeting to determine analysis set classifications may also be held prior to database lock.

In general, all data will be summarized by treatment group with descriptive statistics (number of subjects, mean, standard deviation, minimum, median, maximum, and interquartile range) for continuous endpoints, and frequency and percentage for categorical endpoints.

7.1 Sample Size

The sample size for this study was determined based upon a comparison of the rate of the two-part composite endpoint in the Astagraf XL group compared to the immediate-release tacrolimus group. Assuming a rate of 20% would be observed for the immediate-release tacrolimus group compared to a rate of 10% for the Astagraf XL group, 220 subjects per group are needed to achieve an 80% power to detect a difference between Astagraf XL and immediate-release tacrolimus with a two-sided alpha level of 0.05. The study will enroll 275 subjects/group (550 total) to allow for 20% dropout.

7.2 Analysis Set

Detailed criteria for analysis sets will be laid out in Classification Specifications and the allocation of subjects to analysis sets will be determined prior to database hard-lock.

7.2.1 Full Analysis Set (FAS)

The full analysis set will consist of all subjects who are randomized and receive at least one dose of study drug (Astagraf XL or immediate-release tacrolimus). Subjects with pre-transplant cross-match samples that later demonstrate pre-formed antibody (undetected at the time of transplant), as assessed by the adjudication board, will be included in the FAS but not in the modified FAS (see next section).

7.2.2 Modified Full Analysis Set (mFAS)

The modified full analysis set will consist of all subjects who are randomized and receive at least one dose of study drug (Astagraf XL or immediate-release tacrolimus), and whose pre-transplant cross-match antibody samples do not demonstrate pre-formed DSA for the duration of the study. This will be the primary analysis set for efficacy assessments.

7.2.3 Per Protocol Set (PPS)

The per protocol set will consist of the subset of the FAS who do not experience any major protocol deviations. Final adjudication and assessment of the classification for any protocol deviations will be conducted prior to database hard-lock. Further criteria may be defined in the SAP.

7.2.4 Safety Analysis Set (SAF)

For the statistical summary and analysis of safety data, the safety analysis set (SAF) will be used. The SAF consists of all subjects who enrolled into the study and took at least one dose of study medication.

7.2.5 Pharmacokinetic Analysis Set (PKAS)

Not applicable.

7.3 Demographics and Other Baseline Characteristics

Demographics and other baseline characteristics will be summarized by treatment group for the SAF. Descriptive statistics will be included for continuous endpoints, and frequency and percentage for categorical endpoints.

7.4 Analysis of Efficacy

The analysis of Efficacy will be conducted using the mFAS.

7.4.1 Analysis of Primary Endpoint

7.4.1.1 Primary Analysis

The primary efficacy endpoint is the combined incidence of either DSA or IA on molecular blood profiling at one year or at the conclusion of the study.

The primary endpoint will be analyzed at a single time point, corresponding to end of study and with respect to the formal stopping rule (see Section [7.8.1](#)). The primary analysis of this endpoint will be based on the mFAS. The incidence of the primary endpoint will be summarized by treatment group with frequencies and percentages. Differences between treatment groups will be analyzed using logistic regression with the following covariates: treatment group (Astagraf XL group versus the immediate-release group), the pre-defined randomization stratification factors, recipient age, race, and gender; type of induction therapy, delayed graft function, and pre-transplant cPRA.

For subjects with missing or incomplete endpoint data who did not permanently switch therapy or were discontinued from the study prior to a DSA/IA event, who are lost to follow up, or those who expire for any reason), negative DSA/ IA values will be imputed unless there is an otherwise positive result.

The hypothesis for comparison is as follows:

H0: The probability of incidence for the primary endpoint is the same between patients receiving Astagraf XL and patients receiving immediate-release tacrolimus.

H1: The probability of incidence for the primary endpoint is not the same between patients receiving Astagraf XL and those receiving immediate-release tacrolimus.

Hypothesis testing will be performed using a two-sided test with a 0.05 significance level. The 95% confidence interval for the odds ratio of the primary endpoint between Astagraf XL and twice daily tacrolimus will be included.

7.4.1.2 Sensitivity Analysis

A sensitivity analysis using the FAS will be conducted on the primary endpoint. The same logistic regression analysis described in Section 7.4.1.1 will be used.

Additionally, a sensitivity analysis for mFAS patients will be performed exclusively using assessments with a basis in normal creatinine function.

7.4.1.3 Secondary Analysis

A secondary analysis using the PPS will be conducted on the primary endpoint data. The same logistic regression analysis described in Section 7.4.1.1 will be used.

7.4.1.4 Subgroup Analyses of the Primary Endpoint

Subgroup analyses of the primary endpoint, using the mFAS, will be conducted by patient age, sex, and race as well as donor race.

7.4.2 Analysis of Secondary Endpoints

Risk factor analyses will be conducted for all 15 binary assessments. In addition to the treatment effect, the risk factors assessed will include: manufacturer and type of immediate-release tacrolimus; medication compliance, prior transplantation recipient, IPV of tacrolimus whole blood concentrations; absolute tacrolimus whole blood concentration dose and duration of MMF (or Myfortic equivalent); amount and duration of post-transplant corticosteroid use, type and amount of induction therapy used; age, sex, race, cold ischemia time (CIT), warm ischemia time (WIT), KDPI, DCD status, LD vs. DD status, recipient pre-transplant dialysis status > 3 months (yes/no), donor race, pre-transplant donor kidney *ex vivo* perfusion parameters, degree of HLA mismatch, and pre-transplant cPRA; and the presence of post-transplant bacterial and viral infection (including BK and CMV). Additional risk factors may be included per the SAP.

Binary endpoints will be summarized with frequencies and percentages by treatment group and time point. The incidence of events will be analyzed for treatment group differences at each time point, in addition to overall. Analysis of treatment group differences will be implemented with generalized estimating equations (GEEs) using random effect(s), as necessary, to account for the temporal structure of data collection. This analysis applies to each of the following incidence-based endpoints:

1. DSA formation
2. IA
3. TG

4. Acute and chronic forms of ABMR
5. C1q-binding DSA
6. HLA-DQ DSA
7. DSA IgG₃ isotype
8. Requirement for antibody reduction therapy
9. eGFR at various thresholds (less than 30, 40, 50 mL/min/1.73 m² at one year or later; and a five-point decline)
10. Graft loss (defined as subject death, retransplantation, transplant nephrectomy, or a return to dialysis for at least a 6 week duration)
11. Mortality
12. BPAR (inclusive of ABMR and TCMR)
13. The four-part traditional composite endpoint: graft loss, local BPAR, mortality, and lost to follow-up (note – lost to follow-up will be summarized descriptively only)

GEE models used for analysis of treatment group differences will use the same covariates detailed in Section 7.4.1.1 with the exception of biopsy-based endpoints (i.e., TG and ABMR). In addition to the set of covariates from Section 7.4.1.1 biopsy-based endpoints will also include the covariates of CIT, WIT, KDPI, DCD status, and the three ex vivo perfusion parameters recorded pre-transplant. Similar to the primary endpoint, additional changes/details for the set of covariates will be included in the SAP.

For study purposes, lost to follow-up is defined as a subject failing to complete their final study visit no more than 30 days prior to the scheduled visit, and without a prior incidence of local BPAR, graft loss, or death. The incidence of lost to follow-up will be summarized with frequencies and percentage by treatment group.

The assessments of time to first occurrence for DSA, HLA-DQ DSA, C1q-binding DSA, DSA IgG₃ isotype, IA, TG, select BANFF histology grades (acute and chronic forms of ABMR, acute and chronic active TCMR, borderline changes, and IFTA), graft loss, mortality, local BPAR, and the four-part traditional composite endpoint will be summarized from the date of transplant. For patients who did not experience the endpoint event and/or were lost to follow-up or died prior to reporting the event, they will be censored at the date of their last known assessment/follow-up/death. Summaries will include estimable quartiles of time-to-first event with 95% confidence interval, Kaplan-Meier (KM) figures, and hazard ratios with 95% confidence interval. In the event that the median times are not estimable, the proportion of subjects with no DSA formation at the one and two year time points (as applicable) will be summarized by treatment group. Treatment group differences will be assessed with Cox regression models that account for the same covariates as used in the analogous GEE models.

The type of antibody reduction therapy will be summarized at each time point using frequencies and percentages. Analysis of treatment group differences will be conducted

using multinomial logistic regression and GEEs with the same covariates used in the primary endpoint's model and random effects(s), as necessary.

Ordinal assessments of antibody strength (weak, moderate, and strong) will be summarized at each time point using frequencies and percentages. Analysis of treatment group differences will be done by time point and overall using a proportional odds model and GEEs with the same covariates used in the primary endpoint's model and random effect(s), as necessary, to account for the temporal structure of data collection.

The continuous endpoint of MFI score will be summarized with descriptive statistics by time point. Due to the expected non-normality of errors, an analysis of treatment group differences will be implemented with a semi-parametric, mixed repeated measures model on rank scores using a random effect of subject and the same covariates included in the analysis of Section [7.4.1.1](#). Least square mean (LS Mean) estimates will be provided at each time point and treatment group differences will be assessed at each time point and overall.

Histopathology assessments will be summarized with both descriptive statistics and frequencies and percentages. Raw biopsy scores, including g, t, v, i, cg, ct, ci, cv, ah, ptc, and mm will be summarized as ordinal outcomes. Analysis of treatment group differences will be performed using the same proportional odds model and GEEs implemented for the analysis of antibody strength. The incidence of binary outcomes including ci, ct, and ptc scores greater than 1 will be summarized with frequencies and percentages. Analysis of treatment group differences will be done consistent with the models using GEEs for the other binary endpoints. For biopsy-based analyses, additional covariates will be added to the existing set in order to account for CIT, WIT, KDPI, DCD status, and the three ex vivo perfusion parameters recorded pre-transplant.

Assessments of association between DSA and IA will be analyzed overall and by treatment group with logistic regression models using DSA formation as the response and IA as predictor.

For patients who develop IA or DSA, change in eGFR from the time of diagnosis will be summarized with descriptive statistics by treatment group and by time point. An analysis of treatment group differences will also be made using the same mixed, repeated measures model that is fit for the raw MFI scores.

The binary endpoints (bulleted early in this section) and the persistence of DSA will be analyzed under the subgroups of patients who developed DSA and patients who developed IA. Treatment group differences by time point and overall will be assessed with the same GEE models and covariates detailed in this section.

7.4.3 Analysis of Exploratory Endpoints

Analysis will be performed on the secondary composite endpoint consisting of DSA formation and the presence of TG ($cg > 0$). The same analysis from Section [7.4.1.1](#) will be conducted for treatment group differences. The analysis will be performed using the mFAS population.

The associations between each of HLA-DQ DSA incidence, ordinal DSA strength, DSA formation, C1q-binding DSA, DSA IgG₃ isotype will be analyzed with respect to each other and with IA, TG, acute and chronic ABMR, histopathology, eGFR at various thresholds (less than 30, 40, and 50 mL/min/1.73 m²), ABMR (acute and chronic), TCMR, graft loss, and mortality. Binary GEE models and proportional odds models will be fit for incidence and ordinal strength of HLA-DQ DSA, respectively. Associations will be analyzed between treatment groups and overall as well as across time points. Analogous methods will be used to assess the association between DSA and each component of the traditional composite endpoint.

The incidence of patients with normal and abnormal creatinine assessments and an IA designation will be summarized with descriptive statistics. Concordance between the IA and biopsy results will be summarized with descriptive statistics for each of the normal and abnormal creatinine assessments. Analysis of concordance between the IA and biopsy results will be conducted using Cohen's Kappa for each of the abnormal and normal creatinine assessments.

Percent MFI reduction will be summarized with descriptive statistics by time point. Analysis of treatment group differences will be done using the same semi-parametric, mixed, repeated measures model implemented for raw MFI scores. MFI shift will be summarized with frequencies and percentages and analyzed for treatment group differences using the same proportional odds model used to analyze DSA antibody strength.

Mapping of expression results to known immunological pathways implicated in immune-mediated, kidney transplant injury will be performed using multiple tools including Gene Ontology, Ingenuity's Pathway Analysis™ (Ingenuity Systems, Redwood, CA), TGI's proprietary tool called ImmuneMap, WikiPathways, GSEA Broad, Panther, and NCBI databases such as DAVID. Visualization of networks and hub genes will be done with Cytoscape. Reports on functional pathway mapping will be prepared and provided to Astellas by TGI.

Additional sensitivity and secondary analyses for secondary and exploratory endpoints may be conducted using the PPS or FAS.

7.5 Analysis of Safety

7.5.1 Adverse Events

Adverse events will be coded using the MedDRA. The number and percentage of AEs, SAEs, AEs leading to discontinuation, and AEs related to study drug will be summarized by system organ class, preferred term and treatment group. The number and percentage of AEs by severity will also be summarized. All AEs will be listed.

7.5.2 Laboratory Assessments

For quantitative laboratory measurements obtained during standard of care, descriptive statistics will be used to summarize results and change from baseline by treatment group and time point. Shifts relative to normal ranges from baseline to each time point during the

treatment period with regard to lab tests will also be tabulated. Laboratory data will be displayed in listings.

7.5.3 Histopathology

Data collected based on light microscopy, electron microscopy, and immunofluorescent images will be summarized by treatment group, pathologic designation, and time point stratified by local and central readings.

7.6 Analysis of Tacrolimus Dose and Trough Concentrations

Descriptive statistics (e.g., n, mean, standard deviation, minimum, median, maximum) as well as interquartile range, coefficient of variation, and geometric mean will be provided for tacrolimus dose and whole blood concentrations of tacrolimus for both study cohorts.

Tacrolimus concentrations will be summarized with descriptive statistics. Assumptions and methods for estimation and time point windowing will be detailed in the SAP as appropriate.

Tacrolimus trough by-patient CV and SD estimates will be assessed for association across time and overall with each of the following: the primary endpoint, the secondary composite endpoint of DSA and IA, DSA formation and IA individually, TG, chronic ABMR, C1q-binding DSA, HLA-DQ DSA, DSA IgG₃ isotype, histopathology, renal dysfunction, and the components of the traditional composite endpoint. Analysis details will be included in the SAP.

IPV of dose-adjusted tacrolimus trough levels after the 6 weeks following transplantation will be assessed for treatment group differences. The SAP will detail the analysis methods and time points.

The association between whole blood concentrations and the following endpoints will be assessed: DSA presence, DSA strength, C1q-binding DSA, IgG₃, IA, eGFR, histopathology, and conventional measures of transplant outcomes.

Additionally, the effect of switching product manufacturers during the study will be assessed with tacrolimus concentration. Changes will be assessed between treatment groups and for patients taking bid tacrolimus with the bid tacrolimus group analyzed for differences between those who did and did not switch manufacturers during the study.

7.7 Protocol Deviations and Other Analyses

Protocol deviations as defined in Section [8.1.6](#) will be summarized for all randomized subjects by treatment group and total as well as by site. A data listing will be provided by site and subject. The protocol deviation criteria will be uniquely identified in the summary table and listing. The unique identifiers will be as follows:

PD1 - Entered into the study even though they did not satisfy entry criteria,

PD2 - Developed withdrawal criteria during the study and was not withdrawn,

PD3 - Received wrong treatment or incorrect dose,

PD4 - Received excluded concomitant treatment.

7.8 Interim Analysis (and Early Discontinuation of the Clinical Study)

No formal interim analysis is planned.

7.8.1 Formal Stopping Rule

Given the variability of incidence rates for DSA reported in the literature, a stopping rule has been incorporated into ASTOUND to mitigate the risk of continuing the study under incorrect prior assumptions (Section 7.1). This stopping rule will be based on the incidence of the primary endpoint (combined incidence of either DSA or IA).

Patients will remain on treatment for 12 months or potentially longer (up to a maximum of 24 months). Nevertheless, in order to minimize the risk of conducting a study that could be, in the end, underpowered, a decision tree (Figure 3) will be actuated once 50% of control patients have completed one year of therapy. If, based on the enclosed algorithm, the primary endpoint's event rate in the control arm at that time is high enough for efficacy to be assessed at one year for the totality of subjects entering the study, the trial will continue enrolling and those subjects who, up until that point have completed <12 months of therapy, will be permitted to remain on such until study completion (1 year). However, it is acknowledged that in deploying a potential stopping rule once 50% of patients have completed one year of therapy, that a certain percentage of patients may have progressed beyond one year of therapy by the time the decision algorithm is applied. If this situation should occur, only the one year data for these patients will be included in the efficacy assessment, the exception being if the decision algorithm dictates that the study should continue for an additional year, in which case, the efficacy assessment will be made at 24 months for all patients.

For the decision algorithm, the estimated proportion will be used to calculate the Beta-binomial posterior Bayesian probability that the primary endpoint's incidence rate will, indeed, be at least 20% (see Appendix 12.4 for assumption details).

As mentioned above, a decision to terminate the study early or extend to a second year will be predicated on the event rate in the control arm once 50% of control patients have completed one year of therapy. At that time, the estimated proportion will be used to calculate the Beta-binomial posterior Bayesian probability that the primary endpoint's incidence rate will, indeed, be at least 20%.

If this probability is $\geq 70\%$, the following rules apply:

- 1) The study will continue to enroll to completion.
- 2) The study duration will be such that patients will complete at least one year of study visits.
 - a) Patients who have not yet completed one year of study (at the time of the interim analysis) will complete the study at the 12m visit.
 - b) Patients who have already completed the 12m visit (at the time of the interim analysis) will complete the study at their next scheduled study visit.
- 3) Data analysis will be performed once all patients complete 12 months of study.

[figure not shown]
If this probability is $< 70\%$ and $\geq 30\%$:

- 1) The study will continue to enroll to completion.
- 2) The study duration will be 24 months; patients will complete the study at the 24 month visit.
- 3) Data analysis will be performed once all patients complete 24 months of therapy.

If this probability is $< 30\%$, the study will be terminated at that time (50% of patients completing 12 months of therapy).

- 1) The study will be terminated upon completion of the interim analysis (done when 50% of patients have completed 12 months of therapy).
- 2) Patients will be discontinued from the study at their next scheduled study visit.

Figure 3 Application of Stopping Rule

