12.4 Interim Decision Rule Details

The Interim report stopping rules for this study are based on a Bayesian methodology of the *Beta-Binomial* posterior distribution.

The prior distribution used as the basis of the posterior is the $Beta(\alpha=2, \beta=8)$. This prior was chosen due to its expectation (mean) of 0.20, and therefore remains consistent with the assumption that the twice daily tacrolimus DSA/IA composite endpoint incidence rate is 0.20 (Section 7.1). The variance of the distribution was also analyzed for robustness to the scaling of α and β , holding the expectation constant (mean of 0.20). Note that in this case, the variance of the *Beta* distribution is inversely related to the scaling of parameters. The decision rule cutoff values found in Section 7.8.1 remain robust to scaling of the parameters for anything from 1/1000 to unity (results not shown). Decreasing the variance beyond what is associated with a $Beta(\alpha=2, \beta=8)$ distribution was not considered in order to maintain the conservative nature of weighting prior information.

Let x be the number of occurrences of the DSA/IA composite primary endpoint, n be the number of evaluable subjects at the time of analysis, and p be the actual probability of the primary endpoint's occurrence in the population of twice daily tacrolimus use. Therefore, the posterior probability is based on the assumption that x given n and p is distributed as $Binomial(n, p)$. Therefore given the prior distribution of $p|\alpha, \beta \sim Beta(\alpha = 2, \beta = 8)$ and a binomial distribution for the frequency of the DSA/IA primary endpoint ($x|n, p \sim Binomial[n, p]$), then by Bayes' rule the conditional distribution of p follows as a *Beta-Binomial* posterior of $p|x, n, \alpha, \beta \sim Beta(2 + x, 8 + n - x)$.

The following table [Table 1] illustrates the possible posterior probabilities of $p \geq 0.2$ for the twice daily tacrolimus group given 50% of the planned subjects completed the 12 month follow-up visit ($n = 110$). In particular, the distribution in this case is $p|x, n, \alpha, \beta \sim Beta(2 + x, 118 - x)$.

- CONFIDENTIAL -

Table 1 50% of Subjects Complete 12 Month Visit (n=110)

Incidence of DSA/IA	Observed Proportion	Posterior Probabilities
x	$p=x/110$	$P(p \geq 0.20 x, n, \alpha, \beta)$
10	0.091	0.001
11	0.1	0.003
12	0.109	0.006
13	0.118	0.013
14	0.127	0.024
15	0.136	0.042
16	0.146	0.07
17	0.155	0.11
18	0.164	0.162
19	0.173	0.228
20	0.182	0.305
21	0.191	0.391

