The calculations in the following table and figure show the incidence boundaries for at least 80% power under incidence rates of DSA/IA in the immediate-release tacrolimus arm of 0.04 to 0.19. Values of Astagraf XL less than immediate-release tacrolimus values were investigated exclusively, as values of Astagraf XL being larger than immediate-release tacrolimus are not of scientific interest for this study.

- CONFIDENTIAL -

Table 1 Statistically significant outcomes with at least 80% power.

BID Tac	Astagraf XL			
	N = 220		N = 110	
	Statistical Significance with \geq 80% Power	Percent Decrease	Statistical Significance with \geq 80% Power	Percent Decrease
0.19	≤ 0.093	51.05	≤ 0.059	68.95
0.18	≤ 0.085	52.78	≤ 0.053	70.56
0.17	≤ 0.078	54.12	≤ 0.047	72.35
0.16	≤ 0.071	55.63	≤ 0.041	74.38
0.15	≤ 0.064	57.33	≤ 0.035	76.67
0.14	≤ 0.057	59.29	≤ 0.030	78.57
0.13	≤ 0.050	61.54	≤ 0.025	80.77
0.12	≤ 0.043	64.17	≤ 0.020	83.33
0.11	≤ 0.037	66.36	≤ 0.015	86.36
0.10	≤ 0.031	69.00	≤ 0.011	89.00
0.09	≤ 0.025	72.22	≤ 0.007	92.22
0.08	≤ 0.019	76.25	≤ 0.003	96.25
0.07	≤ 0.014	80.00	NA	NA
0.06	≤ 0.009	85.00	NA	NA
0.05	≤ 0.005	90.00	NA	NA
0.04	≤ 0.001	97.5	NA	NA

- CONFIDENTIAL -

Figure 1 Astagraf XL and immediate-release tacrolimus DSA/IA proportions that are statistically significant with 220 and 110 subjects per group and at least 80% power.

[figure not shown]

Figure 1 illustrates statistical significance with 80% power on the continuum for all points falling above each of the respective lines. For example, any points above the red line represent outcomes of statistical significance with at least 80% power for the full study sample of 220 subjects. The same applies to the black line representing N=110 as the early termination sample size. Therefore, the risk of early termination for the study is all points between each of the two lines in the figure.

This area of risk has been identified and mitigated with the current stopping rules in Section [7.8.1](#) of the study protocol.

13 ATTACHMENT 1: NON-SUBSTANTIAL AMENDMENT 2

ISN/Protocol IDTX-MA-3004 Non-Substantial Amendment 2 May 25, 2018

I. The purpose of this amendment is:

Non-Substantial Changes
1. Revision of molecular profiling categories
DESCRIPTION OF CHANGE
Sub-categories for the molecular profiling endpoints of cAR (clinical acute rejection) and subAR (subacute rejection) were removed throughout the protocol.
RATIONALE:

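### The stated 80% power is a fixed-sample figure: at the planned 20% control rate the stopping rule ends 28% of trials, leaving design power of about 64-71%

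*Protocol*

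**What the plan says.** Protocol 7.1 gives the planning assumptions: "Assuming a rate of 20% would be observed for the immediate-release tacrolimus group compared to a rate of 10% for the Astagraf XL group", "with a two-sided alpha level of 0.05". On these, "220 subjects per group are needed to achieve an 80% power". Enrolment is 275 per group to allow for 20% dropout. SAP 4 repeats the calculation. Neither section mentions the stopping rule.

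Protocol 7.8.1 applies a decision rule when half of the controls have completed one year. It presents the rule as a safeguard, adopted "in order to minimize the risk of conducting a study that could be, in the end, underpowered". There are three branches, set by the posterior probability that the control rate is at least 20%:

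- 70% or more: analysis at 12 months.
- 30% to below 70%: extension to 24 months.
- Below 30%: termination. In the protocol's words, "The study will be terminated upon completion of the interim analysis".

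Appendix 12.4 sets the prior as Beta(2, 8), takes n = 110 at the interim and tabulates the posterior probability for each event count. It says the cutoffs "remain robust to scaling of the parameters for anything from 1/1000 to unity". Appendix 12.5 compares the effects detectable with 110 and 220 per group for control rates of 0.04 to 0.19, and ends: "This area of risk has been identified and mitigated with the current stopping rules".

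SAP 7.9 reports that the interim took place and the study went on under the 12-month branch.

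**The concern.** The rule is binding, and its test value of 20% is the control rate that the sample size assumes. If that assumption is exactly right, the observed rate at the interim falls below 20% about as often as above it, and a shortfall of only three events (19 where 22 are expected) ends the trial. A 28% chance of stopping is therefore built in when nothing is wrong with the planning.

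A power figure that ignores this does not describe the design as written. Neither document gives the chance of stopping at 20%, or power with the rule included. Appendix 12.5 stops just short of the planned rate and treats the rule as the remedy, although at the planned rate the rule is the source of the loss. Anyone who approved or funded the trial on the 80% was not shown this. SAP 4 restates the figure in a version written after the interim, so it could pass unqualified into the study report.

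**Working it through.** **Inputs.** Rates of 20% and 10%, two-sided alpha 0.05 and 220 per group (Protocol 7.1). Interim n = 110 and prior Beta(2, 8) (Appendix 12.4). Termination below 30% (7.8.1). A terminated trial has 110 per arm, and Fisher's exact test is used (Appendix 12.5). The uncorrected chi-square test is shown beside Fisher's.

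**1. Reproduce the stated figure.** The two-proportion formula gives 199 per arm without continuity correction and 219 with it. Exact power at 220 per arm is 0.811 (Fisher) or 0.845 (chi-square). Dropout: 220 / 0.80 = 275. The calculation in 7.1 is correct for a fixed-sample trial.

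**2. Turn the rule into event counts.** The posterior after x events in 110 is Beta(2 + x, 118 − x). The probability that p is at least 0.20 is:

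| x | Probability | Action |
|---|---|---|
| 19 | 0.228 | terminate |
| 20 | 0.305 | extend to 24 months |
| 24 | 0.659 | extend to 24 months |
| 25 | 0.737 | analyse at 12 months |

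These match Appendix 12.4. The trial terminates at x ≤ 19.

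**3. Chance of each branch when the true control rate is 0.20.** With X ~ Binomial(110, 0.20):

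- P(X ≤ 19) = 0.281, terminate.
- P(20 ≤ X ≤ 24) = 0.449, extend.
- P(X ≥ 25) = 0.271, analyse at 12 months.

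The chance of termination is 0.481 at a true rate of 0.18, 0.139 at 0.22 and 0.035 at 0.25.

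**4. Power with the rule included.** This is exact enumeration over the 110 interim controls, the other 110 controls and the 220 Astagraf XL patients, at 20% versus 10%:

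| | Fisher | Chi-square |
|---|---|---|
| No rule, 220 per arm | 0.811 | 0.845 |
| Continue and reject | 0.636 | 0.656 |
| Stop, then reject at 110 per arm | 0.035 | 0.053 |
| Total if stopped trials are tested | 0.671 | 0.708 |
| Loss if a stopped trial is a failure | 0.175 | 0.190 |
| Loss if it is tested at 110 per arm | 0.140 | 0.137 |

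The loss is 14 to 19 points.

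**5. Ceiling.** Only 1 − 0.281 = 0.719 of trials continue. If every one of them rejected, the total would still be at most 0.719 + 0.035 = 0.754 (Fisher) or 0.719 + 0.053 = 0.772 (chi-square). The 24-month branch cannot lift this, because it applies only to trials that were not stopped.

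**6. Prior scaling.** With the prior Beta(2s, 8s), the probability at x = 20 is:

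| s | Probability at x = 20 | Terminate at |
|---|---|---|
| 1 | 0.305 | x ≤ 19 |
| 0.5 | 0.301 | x ≤ 19 |
| 0.1 | 0.298 | x ≤ 20 |
| 0.001 | 0.297 | x ≤ 20 |

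Within the range that Appendix 12.4 calls robust, the termination bound moves from 19 to 20. P(stop) at 20% rises from 0.281 to 0.281 + 0.087 = 0.368. The 12-month bound stays at 25.

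**The case against.** **The calculation in 7.1 is right.** It is, as a fixed-sample calculation, and step 1 reproduces it. What is missing is an operating characteristic of the design that contains the rule.

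**Stopping on a low control rate is deliberate.** A sponsor may accept that trade. The rule was meant to catch a wrong assumption, however, and it also stops more than a quarter of trials whose assumption is right. That cost should have been stated.

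**Appendix 12.5 is about control rates below 0.20, so omitting 0.20 is within its scope.** This is fair as a reading of its stated purpose. It still leaves the planned rate unexamined, and its closing sentence claims more than its table shows.

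**A terminated trial might have more than 110 per arm.** Neither document describes such an analysis, and patients would leave at their next scheduled visit. Reaching 80% overall would take about 180 per arm after stopping by chi-square, or between 200 and 220 by Fisher.

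**The robustness point is thin.** One boundary count moves, and only when the prior is scaled down strongly. The prespecified Beta(2, 8) rule is unaffected. But the claim covers the whole range down to 1/1000 and fails within it.

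**The interim is past.** This stands, and it limits the point. No remaining analysis changes.

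Three stronger readings are tempting, and the documents do not support them:

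- A reader might infer that a null result should be read against 64-71% power. That figure averages in stopped trials, and SAP 7.9 shows this trial was not one. Given the 12-month branch (x ≥ 25 of 110), power at 20% versus 10% is 0.956 (Fisher) or 0.969 (chi-square).
- A reader might take the 80% as power conditional on not stopping. That quantity is 0.636 / 0.719 = 0.885 (Fisher) or 0.656 / 0.719 = 0.912 (chi-square).
- A reader might take half of the controls as half of the 275 enrolled, which gives a higher chance of stopping. Appendix 12.4 sets the number at 110.

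**Conclusion.** The point holds as a misdescribed design characteristic. The 80% in Protocol 7.1 and SAP 4 is fixed-sample power, and the design with its binding stop does not have it. At the planned rates, 28% of trials terminate. Power is about 64-66% if termination counts as failure, or 67-71% if the terminated trial is tested at 110 per arm. The ceiling in step 5 keeps it below 80% even on the most favourable view of the trials that continue.

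These figures assume 220 evaluable patients per arm, 110 controls at the interim, 110 per arm after stopping, and rates of 20% and 10% that also apply at 24 months. With all 275 per arm evaluable, and stopped trials tested at 110 per arm, power is 71% (Fisher) or 74% (chi-square), still short of 80%. Protocol 7.1 does not say whether the 20% is a one-year or a two-year rate. If it is a two-year rate, the one-year rate is lower and the chance of stopping exceeds 28%.

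The robustness statement in Appendix 12.4 is also wrong as written, by one event at the termination bound. Nothing here calls into question the interim decision taken or the analysis still to be done.

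**What to change.** - **Protocol 7.1 and SAP 4:** label the 80% as *fixed-sample power, ignoring the stopping rule*. Add that the chance of termination at a 20% control rate is 28% and that unconditional power is about 64-71%. State the assumptions: 220 evaluable per arm, n = 110 at the interim, 110 per arm after stopping, and 20% and 10% also holding at 24 months.
- **Appendix 12.5:** extend the risk analysis to a control rate of 0.20, give the probability of stopping there, and replace the statement that the risk is mitigated with the quantified risk.
- **Appendix 12.4:** correct the robustness claim. With the prior scaled by 0.1 or less, the termination bound moves from 19 to 20 and the chance of stopping at 20% rises from 28% to 37%.
- **Study report:** if design power is quoted, describe it as a pre-trial design characteristic, and do not use 64-71% to interpret a null result.

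The cost is wording only. No data, test or patient procedure changes. The stated power becomes less favourable.
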